9.8.1.1 Project management

The clinical project manager is responsible for the following (selected items):

- Development of the clinical investigation plan and possible amendments.
- Coordination of all study-related activities dedicated to the sponsor.
- Support of investigational sites during the study (obtaining ethic committee votes, etc.).
- Continuous information of investigational sites and clinical monitors on study progress.
- The clinical project manager is supported by other staff members of the sponsor (e.g. in-house clinical research associates, data assistants, data base managers).

9.8.1.2 Data Management

The data manager is responsible for the following items (selection of items):

- Development and maintenance of the clinical data management system (CDMS; iMedNet of the company MedNet Solutions Inc, Minnetonka, MN 55305 USA).
- Development of the data management plan.
- Development of the CRF user guide.
- Data management.

9.8.1.3 Biostatistician

The statistician is responsible for the following items (selection of items):

- All statistical aspects within the clinical investigation plan.
- Statistical analysis for clinical investigation report.

The statistician will be supported by other staff members of the sponsor.

9.8.1.4 Monitor

The sponsor names clinical monitors for each participating investigational site prior to initiation of the respective site. Names and contact data will be provided to the investigational sites in due time. In case of changes, the investigational site will be informed by the sponsor. An adequate monitoring will be ensured by the sponsor. Monitoring will be conducted according to the SOPs of the sponsor. Responsibilities of the clinical monitors are described in section 10 of this document.

9.8.2 Responsibilities of the investigators

9.8.2.1 Investigator

The study shall be conducted by qualified investigators.

Rights and duties of the investigators are specified in the clinical investigation plan and are further regulated in the contract for study conduct. The principal investigator named in the study contract may share the rights and duties with investigators and other staff at the investigational sites. Nevertheless, the principal investigator retains the main responsibility for proper study conduct with respect to the following duties:

- Registration of the study to the bodies responsible for the investigational site (e.g. hospital administrative department).
- Notification to competent authority (if applicable) responsible for the investigational site.

- If required, obtaining of a positive vote of the ethics committee responsible for the investigational site.
- Adverse Event reporting according to the clinical investigation plan.
- Recruitment of suitable patients in an adequate time frame.
- Patient information and obtaining of written informed consent of the patient according to the requirements of the CIP.
- Safe and efficient use of devices.
- Inform the sponsor about new study team members before authorizing them for study related activities.
- Provide the sponsor with required documentation for assessing the qualification of study team members.
- Authorize co-investigators only after documented adequate study specific training.
- Conduct of the study according to the CIP.
- Data collection and data entry in accordance with the requirements of the CIP.
- Providing supporting material, if necessary.
- Submission of safety reports and protocol deviations to ethics committee and competent authorities (if applicable).
- Support of monitoring and auditing activities.
- Confidential treatment of all study-related documents and information.

In case the principal investigator (or authorized staff) does not fulfill the requirements defined, the sponsor is entitled to exclude the respective investigational site or principal investigator from further study participation.

9.9 Possible influencing factors on outcome or interpretation of results

No factors that could influence the outcome or interpretation of the results are known at this time.

10 MONITORING PLAN

The responsibility of BIOTRONIK as sponsor is to ensure protocol and regulatory compliance through proper monitoring of the study. BIOTRONIK is required to ensure that the Renamic Neo programmer, software NEO 2001.A and ECG cable PK-222-L are used under the immediate direction of an investigator. As the investigator, the physician is responsible for conducting the study in accordance with the signed clinical trial agreement, clinical investigation plan, applicable laws, local regulations and any conditions of approval imposed by the reviewing EC.

The entries in the CRF will be reviewed and source data verified at the investigational site by monitors (authorized BIOTRONIK personnel, Clinical Research Associates (CRAs), or by authorized BIOTRONIK designees) to ensure that the investigator and the clinical investigation team conducts the clinical investigation in accordance with the CIP, The Declaration of Helsinki, ISO 14155, and applicable laws and regulations to ensure adequate protection of the rights, safety and wellbeing of subjects and the quality and integrity of the resulting data.

A monitor will visit the study site periodically during the study. All actively enrolling sites will have at least an initiation visit, one early monitoring visit after the first patients have been enrolled in order to detect and prevent systematic errors in study conduct or documentation, and a close-out visit. Additional monitoring visits will be conducted based on risk related criteria such as e.g. recruitment rate and documentation quality. Details on criteria for initiating monitoring visits as well as strategy and extent of source data verification are subject to a detailed monitoring plan developed by BIOTRONIK as an internal document.

Monitoring visits will assure, amongst others, that the facilities are still acceptable, that the CIP is being followed, that the EC/CA has been informed about approved CIP changes as required, that records on study conduct and data collection are complete and present, that appropriate and timely reports have been made to the sponsor and the authorities, and that the investigator is carrying out all agreed activities.

Assessments of the study site will include but will not be limited to the following:

1. Completion and submission of the required electronic case report forms (CRFs) and other applicable study documentation
2. Continued acceptability of the facilities, including storage and maintenance of investigational inventory
3. Adherence to the clinical investigation plan
4. Adherence to current version of ISO 14155 and applicable local regulations and laws

If a monitor becomes aware that an investigator is not complying with the requirements mentioned above, the monitor is obliged to notify BIOTRONIK study management. BIOTRONIK will evaluate the non-compliance and issue corrective actions, discontinue enrollment or as a last measure close the clinical investigational site (see section 14 and 20).

11 STATISTICAL CONSIDERATIONS

11.1 Statistical design, method and analytical procedures

For continuous variables descriptive statistics (mean, standard deviation, median, quartiles, minimum, and maximum) will be calculated. For nominal and ordinal variables absolute and relative frequencies will be calculated based on non-missing data. Ordinal variables are described similar as continuous data (minimum, median, quartiles, and maximum) or by absolute and relative frequencies based on non-missing data of each category. Further details will be provided in the separate Statistical Analysis Plan (SAP).

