5.2 Clinical data

For the Renamic Neo system, no clinical data are available yet.

The preceding programmer Renamic has been used in many BIOTRONIK sponsored clinical studies, e.g.

- QP ExCELS (NCT03155724)⁸
- Eluna Family Sentus BP Master Study (NCT02059629)⁹
- Matrix (NCT01774357)¹⁰
- BIO|MASTER.Ilivia / Plexa Family (NCT02774616)¹¹
- BIO|MASTER.BioMonitor 2 (NCT02565238)¹²

Renamic was granted CE approval in Sep 2010 and was predominantly used in any BIOTRONIK study starting from January 2015 onwards that supported regulatory approval. Renamic was not explicitly investigated in these studies, but the positive results of these studies imply a correct and safe functioning of this programmer generation. As the functioning of the Renamic Neo is highly similar to that of the Renamic it is expected that the complication rate will be very low.

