5.3 Justification

The main objective of this study is to provide evidence for the clinical safety, performance and usability of the Renamic Neo programming device including software and PK-222-L ECG cable.

The study is designed in a use case centric approach, i.e. it follows the usage of Renamic Neo programmer system and not the individual patients, so that a sufficient number of use cases is collected that allows for the detection of possible adverse device effects and device deficiencies caused by the programmer.

Patients will stay in the study only for implantation and PHD or follow-up and are terminated directly afterwards as ADEs and DDs related to the programmer are expected to occur only during the use of the programmer.

As the Renamic Neo system will be used for the first time in clinical routine, a significant number of use cases from implantation – given that the PSA module might be used – and follow-ups shall be included in this study. Please refer to section 11 for the justification of the sample size calculation.

Approximately 10 clinics with 2-3 Renamic Neo systems each are planned to participate. The multi-centric design will ensure that different environments in which the programmer is placed and used as well as potential hospital specific differences in programmer handling and usage are covered. While just several sites would be sufficient for that purpose, approximately 10 sites will be involved in order to realize a fast study completion. Depending on the special requirements of the sites to use the programmer at different locations at the same time, sites will receive 2-3 Renamic Neo device systems respectively. This results in an approximate number of 20-30 investigational devices.

To cover a broad range of programmer functionalities the device will be used during implantations including PSA usage, if applicable, and follow-up visits. Furthermore, the

enrollment of patients will not be restricted to any subgroup or indication in order to cover use cases for the different CRM devices.

The endpoints adverse device effects and device deficiencies are selected to analyze the safety of the Renamic Neo system and to identify possible residual risks of the programmer. Based on rare observations of events caused by the programming device in the past, only a small number of events are expected. Therefore, no power calculation and no hypothesis for the event-free rate can be provided.

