7.2.2 Endpoints

In this study the number of adverse device effects and device deficiencies (DD) that occur in patients, users or other persons will be evaluated. Definitions are given in section 18. The investigator is asked to report any ADEs or DD that occurred during implantations and follow-ups.

- Number of adverse device Effects / device deficiencies per number of implantations
- Number of adverse device Effects / device deficiencies and per number of follow-up cases

ADEs will be adjudicated by an internal adjudication board, whereby the seriousness and device relatedness will be re-examined. If any amply documented external physical influence (e.g. accident, general power blackout) or medical AE caused the ADE, it does not contribute to this endpoint.

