11.2.1 Implantation

With reference to a statistical approach for such situations recommended by Viechtbauer et al. [Viechtbauer W et al. J Clin Epidemiol. 2015; 68:1375-9], a sample size of 50 documented implantations using a Renamic Neo would allow identifying at least one/two/three ADEs or DDs with 92 % / 72 % / 46 % confidence if any problem related to the Renamic Neo exists with 5 % probability in the population.

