### **10.5. Descriptive Analyses**

For specification "Notes = descriptive", see general definitions in chapter 5.1.

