### 11.1. Analysis Set and Data Selection

All analyses are performed for patients in the PHD & follow-up analysis set using a specific data selection after implantation.

All analyses from chapter 10 ADE and DD Endpoints - Implantation are repeated for these data.

---

 analysis set PHD FUP SAR = Yes and PRUCASE = PHD / Follow-up

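### The ADE and DD endpoints are planned as counts and percentages with no measure of precision, although few events are expected; exact confidence limits should be added, after the any-ADE flag is corrected

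*Protocol*

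**What the plan says.** Protocol 7.2.2 defines two endpoints: "Number of adverse device Effects / device deficiencies per number of implantations" and "Number of adverse device Effects / device deficiencies and per number of follow-up cases". Protocol 7.2.1 declares no hypothesis and no primary endpoint, and 11.5 sets no pass/fail rule.

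For the analysis, protocol 11.1 states: "For nominal and ordinal variables absolute and relative frequencies will be calculated based on non-missing data". SAP 5.1 repeats this. Its template table for a yes/no variable shows the number non-missing, the absolute frequency and the relative frequency. SAP 10.2 specifies case listings of adjudicated events, four patient-level flags (*any ade*, *any sade*, *any dd*, *any ade dd*) and matching event counts. For how to summarise them, SAP 10.5 says "see general definitions in chapter 5.1", and 10.6 adds no test. For PHD and follow-up, SAP 11.1 says: "All analyses from chapter 10 ADE and DD Endpoints - Implantation are repeated for these data". Neither document plans a confidence interval or upper limit for any of these rates.

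On the expected numbers, protocol 5.2 says "it is expected that the complication rate will be very low" and 5.3 says "only a small number of events are expected". Neither section gives a figure. Protocol 7.1 gives the purpose as evidence to support regulatory approval, including the evaluation of residual risks.

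The sample size rests on detection probabilities at a 5% problem rate. Protocol 11.2.1 takes "a sample size of 50 documented implantations using a Renamic Neo" and states 92%, 72% and 46% for at least one, two and three events. Protocol 11.2.2 takes 100 PHD/follow-up cases and states 99%, 96% and 88%.

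**The concern.** When few events are expected, the observed percentage says little and the upper confidence limit says most. A table row of 0 of 50 (0.0%) and one of 0 of 100 (0.0%) look alike, yet they leave different rates open. The study is meant to speak to residual risk, and the rate still compatible with the data is the quantity that does so. No planned table produces it.

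The detection probabilities in protocol 11.2 do not fill the gap. They are fixed in advance at one assumed rate and the planned case numbers. They do not adapt to the numbers achieved, and they give no interval once one or two events have been seen.

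**Working it through.** **Inputs.** n = 50 implantations (protocol 11.2.1); n = 100 PHD/follow-up cases (11.2.2); assumed problem probability 5% (both sections). The two-sided 5% level in protocol 11.3 makes 95% the natural confidence level. Under protocol 9.1 a patient is enrolled either for implantation with PHD or for one follow-up, so within each analysis set one patient corresponds to one use case and a binomial model for the patient-level flags is reasonable.

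**Step 1: the plan's own figures.** P(X ≥ r) = 1 − Σ_{k<r} C(n,k) p^k (1−p)^(n−k), with p = 0.05.

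| n | r = 1 | r = 2 | r = 3 | Protocol |
|---|---|---|---|---|
| 50 | 92.3% | 72.1% | 46.0% | 92 / 72 / 46 |
| 100 | 99.4% | 96.3% | 88.2% | 99 / 96 / 88 |

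All six reproduce.

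**Step 2: limits for zero events.** One-sided 95% upper limit: 1 − 0.05^(1/n). Two-sided 95% upper limit: 1 − 0.025^(1/n).

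- n = 50: 1 − 0.05^(1/50) = 5.8%; 1 − 0.025^(1/50) = 7.1%.
- n = 100: 1 − 0.05^(1/100) = 3.0%; 1 − 0.025^(1/100) = 3.6%.

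**Step 3: comparison with the 5% planning rate.** At a true rate of 5%, zero events has probability 0.95^50 = 7.7% for implantations and 0.95^100 = 0.6% for PHD/follow-up. So 0/50 excludes 5% only at 92.3% confidence, short of 95%, while 0/100 excludes it at 99.4%.

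**Step 4: one event.** Clopper-Pearson two-sided 95% limits: 1/50 = 2.0% (0.05% to 10.6%); 1/100 = 1.0% (0.03% to 5.4%). A single PHD/follow-up event would bring 5% back inside the two-sided interval.

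**Step 5: how likely is a zero count?** The documents give no expected rate, so the following rates are assumptions. P(0 events) = (1−p)^n.

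| Assumed rate | n = 50 | n = 100 |
|---|---|---|
| 1% | 61% | 37% |
| 0.5% | 78% | 61% |
| 0.1% | 95% | 90% |

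If the true rate is 1% or lower, a zero count is an ordinary result.

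**Step 6: can the flags carry an interval as coded?** SAP 10.2 labels *any ade* as covering serious and non-serious effects, but footnote 16 sets it to Yes only when AERELSET = Yes and AESER = No. A patient whose only ADE is serious would be coded No, and an upper limit on that flag would be too low for what its label claims. Footnote 20 puts the same condition on the count *n ade*. Footnote 19 (*any ade dd*) does not filter on seriousness.

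**The case against.** The strongest case on the other side is that the study is openly exploratory. Protocol 11.2 doubts that there will be enough events for inference, 11.5 has no pass/fail rule, and the plan puts its weight on discussing what kinds of events occurred and how. SAP 10.2 supports this with listings by use case, device and programmer serial number. Protocol 11.2 already implies what zero events would mean at a 5% rate, and any reader can compute an exact limit from the N and count in the tables.

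Much of this stands. The listings are a real part of the analysis, and nothing planned is wrongly computed. But an exact interval needs no hypothesis and tests nothing, so it does not conflict with an exploratory design. If no event occurs, the listings are empty and there is no event to discuss. A limit that readers can derive for themselves is still better reported where the regulatory reader will look.

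Three stronger readings are tempting and are not supported:

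- A reader might infer that a zero count will be presented as proof of safety. No rule in either document turns a zero count into a claim.
- A reader might infer that near-zero counts are forecast. The protocol says only that events will be few and complications very low. The endpoint also includes DDs, which under protocol 18.3 cover malfunctions, use errors and inadequate labelling and may be more frequent.
- A reader might take the entry for confidence interval in the SAP abbreviation list as a trace of a dropped analysis. The list also holds AF and SOP, which no SAP analysis uses, so it shows nothing either way.

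**Conclusion.** The gap is real and modest. The only endpoints are reported without precision, and at the planned numbers the missing information is material: zero events would leave rates up to 7.1% open for implantations and 3.6% for PHD/follow-up (two-sided 95%), on opposite sides of the protocol's 5% planning rate. The sample-size figures are correct, and a reader should not infer a flaw in the sample size or in a test.

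The limits assume the planned case numbers and independent use cases. With about 10 sites, 20 to 30 programmers and problems expected to lie mainly in software, clustering by site, programmer or software version could make them too narrow. They apply to the patient-level flags, not to the event counts, for which a patient can contribute more than one event.

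**What to change.** 1. **Correct the flag first.** Change SAP footnote 16 so that *any ade* = Yes whenever AERELSET = Yes, regardless of AESER, as its label says. Align footnote 20 for *n ade* in the same way.
2. **Add the interval.** In SAP 10.5, and through it chapter 11, add: *For any ade, any sade, any dd and any ade dd, the exact (Clopper-Pearson) two-sided 95% confidence interval is reported next to the relative frequency, separately for implantation and for PHD/follow-up. If no event occurs, the upper limit is stated in the SAR and CIR.*
3. **Add a caveat.** Note that the limits assume independent use cases and may be too narrow if events cluster by site, programmer or software version.

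The cost is one table column, two or three SAP sentences and two footnote corrections. No new data, test or hypothesis is needed. Protocol 11.8 allows the SAP to be updated before CDMS freeze or closure.

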11.2 Sample size

No hypotheses can be pre-specified for this clinical investigation, which is completely exploratory.

This clinical investigation should be able to identify unforeseen safety problems. While it is unlikely that the number of ADEs or DDs will be sufficient for inferential statistical conclusions, a discussion of the types of events and of the circumstances of their appearance might reveal indicators for hidden risks and trigger further dedicated investigations or statistical tests to substantiate such findings.

Unforeseen safety problems are more likely related to software problems between Renamic Neo and implanted devices but less likely to hardware problems of the Renamic Neo. Thus, the sample size is related to use cases per implantation, pre-hospital discharge, and follow-up but not to the total number of Renamic Neo devices.

11.2.1 Implantation

With reference to a statistical approach for such situations recommended by Viechtbauer et al. [Viechtbauer W et al. J Clin Epidemiol. 2015; 68:1375-9], a sample size of 50 documented implantations using a Renamic Neo would allow identifying at least one/two/three ADEs or DDs with 92 % / 72 % / 46 % confidence if any problem related to the Renamic Neo exists with 5 % probability in the population.

11.2.2 Pre-hospital discharge and follow-up

Because of the short study duration, no patient is expected to provide data from implantation or pre-hospital discharge on the one hand and follow-up on the other hand. Thus, all data are from other patients, i.e. independent samples when there is no effect of a specific Renamic Neo device effect as discussed before.

Unforeseen problems that require implant programming adjustments will be more relevant during follow-up visits. Thus 100 such use cases will be investigated. Thereby, at least one/two/three ADEs or DDs would be identified with 99%/96%/88% confidence if any problem related to the Renamic Neo exists with 5% probability in the population.

11.3 Level of significance and the power of the study

Because there are no pre-specified hypotheses, all analyses will be exploratory. For inferential analyses, a two-sided p-value less than 5% will be considered statistically significant. In accordance to the exploratory approach there will be no adjustment for multiplicity.

11.4 Expected drop-out rate

Patients that drop-out prior to any use of the Renamic Neo system investigation, e.g. withdrawal just after enrollment, will be replaced. Based on this definition, no drop-outs are expected.

11.5 Pass/fail criteria

There are no pass/fail criteria. Any potential ADEs or DDs will be analyzed and discussed.

11.6 Provision for an interim analysis

There is one planned interim analyses for internal purposes. Except for safety reasons no investigator is informed about the results and, thus, no bias is expected. There will be no adjustment for multiplicity.

11.7 Termination criteria

There is no termination of the clinical investigation on statistical grounds.

